#### **6.6.2 Prohibited concomitant therapy**

G-CSF is permitted for neutropenic fever and/or when clinically indicated.

Concomitant use of sargramostim (GM-CSF), other anti-cancer therapies, including radiation, thalidomide, or other investigational agents is not permitted while subjects are receiving study drug during the treatment phase of the study.

## **6.7 Discontinuation of Study Treatment**

Treatment will continue for 12 weeks of treatment or the occurrence of any of the following events.

- Disease progression as defined by IWG
- Adverse event(s) that, in the judgment of the Investigator, may cause severe or permanent harm or which rule out continuation of the treatment regimen.
- Toxicity that delays the start of the next cycle by more than 4 weeks.
- Discontinuation of lenalidomide for any reason.
- Major violation of the study protocol.
- Withdrawal of consent

- Lost to follow up
- Death
- Suspected pregnancy

## **6.8 Follow-Up**

Subjects who discontinue treatment for any reason will have a discontinuation from study drug visit and a 30 days ( $\pm$  7 days) post-drug discontinuation visit evaluations per the Schedule of Assessments, Section 2. In addition, off study follow-up evaluations for anti-cancer treatments and survival will be obtained every 3 months per the Schedule of Assessments, Section 2.

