### **5.1.2 Secondary Objectives**

- The primary clinical efficacy parameter for these patients will be transfusion independence.
- The secondary efficacy parameters for the study will be the remaining criteria as defined by the IWG. The following parameters also will be assessed:
  - Time to disease progression
  - Overall and progression-free survival

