### **5.2.2 Secondary Endpoints**

- Response will be evaluated **every 4 weeks during the first 12 weeks** of therapy for each of the 56 transfusion-dependent, non-del(5q) low/Int-1 risk MDS patients. Treatment will be stopped and the patient will be taken off the protocol in case of no response or stable disease by 12 weeks. International Working Group (**IWG 2006**) criteria will be used for response evaluation. The proportion of TI will be calculated and an exact 95% confidence interval of TI proportion will be estimated.
- The percent of major and minor responses in erythroid, platelets, neutrophils will also be calculated as the secondary endpoints.

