### **6.1.1.3**

The starting dose of REVLIMID® will be 10 mg days 1-28 with the first dose reduction going to 5 mg days 1-28 of a 28 day cycle. Therapy will cease if there is no response after 12 weeks. Patients responding to treatment will continue on Revlimid® until disease progression or unmanageable toxicities.

- Based on previous trials in del 5q MDS patient one hundred percent of patients reported at least one adverse event; 89% (131/148) experienced at least one grade 3/4 adverse event. Eighty percent required a dose delay and/or reduction for toxicity during the study. Thirty-four percent required a second dose delay/reduction. Dose adjustment recommendations for neutropenia and thrombocytopenia are provided in product labeling. Patients should have complete blood counts monitored weekly for the initial 12 weeks and at least monthly thereafter. Thromboembolic events were rare in the Revlimid® studies in MDS patients with deletion 5q cytogenetic abnormalities. However, in recently reported trials conducted in multiple myeloma, a significantly increased risk of deep venous thrombosis and pulmonary embolism was observed in patients treated with Revlimid® combination therapy. An elevated risk of thrombosis has also been reported when erythropoietin is used during Revlimid® treatment. The role of prophylactic anticoagulation and/or antiplatelet therapy with Revlimid® has not been adequately assessed. Any prophylactic measures should be prescribed after a careful assessment of individual risk factors.
- Patients with serum creatinine above 2.5 mg/dl were excluded from the studies. Because Revlimid® is predominately excreted by the kidney, renal function should be carefully monitored.
- Females should be advised to avoid pregnancy while taking Revlimid®. Revlimid is an analogue of thalidomide, a known human teratogen that causes severe human birth defects. Additional

reproductive toxicity studies will be performed to assess any potential Revlimid® teratogenicity. Only prescribers and pharmacists registered under the RevAssist® program can prescribe or dispense Revlimid®. Patients must agree to comply with the RevAssist® program requirements.

[figure not shown]

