**8.5 Failure:**

Death during treatment or disease progression characterized by worsening of cytopenias, increase in the % BM blasts, or progression to an MDS FAB sub-type more advanced than pre-treatment.

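### Progression-free survival and time to progression are secondary objectives, but no progression status is collected after the 30-day visit, and most patients may have stopped at week 12

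*Combined protocol and SAP*

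**What the plan says.** Section 5.1.2 lists "Time to disease progression" and "Overall and progression-free survival" among the secondary objectives. The synopsis and Section 8.2 repeat both.

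Section 5.2.2 sets the week-12 rule: "Treatment will be stopped and the patient will be taken off the protocol in case of no response or stable disease by 12 weeks". Section 11.2 repeats it. Responders are treated differently (Section 6.1.1.3): "Patients responding to treatment will continue on Revlimid® until disease progression or unmanageable toxicities".

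Section 6.8 covers everyone who stops: "Subjects who discontinue treatment for any reason will have a discontinuation from study drug visit", then a visit 30 days (± 7) after the last dose. Beyond that, "off study follow-up evaluations for anti-cancer treatments and survival will be obtained every 3 months". The two rows of the Section 2 schedule that belong specifically to follow-up name the same two items.

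Section 8.5 counts a death on treatment as failure, and also "disease progression characterized by worsening of cytopenias, increase in the % BM blasts, or progression to an MDS FAB sub-type more advanced than pre-treatment". Section 8.6 defines transformation to AML by a blast count of at least 20%. The only repeat marrow in Sections 2 and 6.1.1 is at discontinuation, when needed to confirm a complete response. Section 11 contains no definition, censoring rule or analysis for TTP or PFS.

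**The concern.** Both endpoints need a date of progression, or a date on which the patient was last known to be free of it. For patients stopped at week 12, the last protocol visit that could supply either is the 30-day visit, at about week 16. Responders remain under observation until they progress or stop for toxicity. Whether later progression can be seen therefore depends on the week-12 response, which is itself an outcome and plausibly related to prognosis.

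With the data as planned, the analyst has two simple options:

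- Censor stopped patients at about week 16. The later part of the curve then describes mainly responders, and the usual assumption that censored patients resemble those still at risk is doubtful.
- Keep stopped patients in the PFS analysis and count only death. Each missed progression is then replaced by a later death or censoring date, so recorded PFS can only equal or exceed true PFS.

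A whole-cohort TTP or PFS figure would then probably look better than the cohort's true course.

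**Working it through.** **Step 1. What follow-up can supply, by patient group.**

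| Period | Stopped at week 12 | Responders continuing |
|---|---|---|
| To week 12 | Counts, transfusions, examination | Same |
| Discontinuation and 30-day visits | Counts, transfusions, examination | Not yet reached |
| After about week 16 | Survival and later anti-cancer treatment only | Counts and transfusions each cycle until progression or toxicity |

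The last assessment for a patient stopped at week 12 falls at 84 + 30 = 114 days, or 114/7 = 16.3 weeks (± 1 week). Section 8.9 adds reviews at 16 weeks and 1 year, but of transfusions only, and Section 6.8 does not provide for collecting them off study.

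**Step 2. Reproduce the source rates.** Section 4.7 gives the MDS 002 results in non-del(5q) low/Int-1 patients.

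- Transfusion independence: 56/214 = 26.2%, stated as 26%.
- Haematologic improvement: (56 + 36)/214 = 92/214 = 43.0%, stated as 43%.

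Both reproduce.

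**Step 3. Expected number stopped at week 12.** Section 5.2.2 evaluates response for "each of the 56 transfusion-dependent, non-del(5q) low/Int-1 risk MDS patients". Number stopped = 56 × (1 − response rate).

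- Response means haematologic improvement: 56 × (1 − 92/214) = 31.9, about 32 (57%).
- Response means transfusion independence: 56 × (1 − 56/214) = 41.3, about 41 (74%).

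Treating these rates as true, the exact binomial probability that more than 28 of 56 stop is 0.82 in the first case and above 0.999 in the second.

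**Step 4. Allow for progression already seen by the 30-day visit.** The documents give no TTP distribution. Assume exponential TTP with a median m of 12 to 36 months, the same in stopped patients as in the rest. The last assessment is at 114/30.44 = 3.75 months. The share still progression-free then is 2^(−3.75/m): 0.805 for m = 12 and 0.930 for m = 36.

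| Response rate | Stopped | Later progression unobserved, m = 12 | m = 36 |
|---|---|---|---|
| 43% | 57.0% | 0.570 × 0.805 = 46% (25.7 of 56) | 0.570 × 0.930 = 53% (29.7 of 56) |
| 26% | 73.8% | 0.738 × 0.805 = 59.5% (33.3 of 56) | 0.738 × 0.930 = 69% (38.5 of 56) |

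If stopped patients progress faster than assumed, more events fall before week 16 and these shares are smaller. Responders who stop for toxicity enter the same limited follow-up and are not counted here, which works the other way.

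**The case against.** - **The size is a projection.** The documents state no expected week-12 stopping rate. The 43% in MDS 002 includes patients with at least a 50% reduction in transfusions, whereas Section 8.11 asks for at least 4 fewer units per 8 weeks, so the rates do not carry over exactly. A reader might infer that progression is unobserved in most patients as a matter of fact. Step 4 does not support that: under the 43% rate the share is about half. This objection stands.
- **The plan prescribes no censoring.** A reader might infer that the protocol censors these patients at week 12. It does not; Section 11 is silent. The two options above are what the data would allow. Later anti-cancer treatment is recorded and could serve in a sensitivity analysis, though only as a proxy.
- **The direction of bias is not proven.** No figure in the documents links week-12 non-response to later progression. The nearest evidence is the thalidomide pilot in Section 4.4: patients off study before week 12 were at higher risk (p = 0.002) with more blasts (p = 0.003), and responders had fewer blasts (p = 0.016). That is a different drug, and the comparison is of baseline features. It supports likely, not certain. Only under death-only counting is the direction fixed, by arithmetic.
- **Follow-up blood counts may exist.** The haematology row of the schedule can be read as reaching the follow-up column. The marks look shifted, since footnotes about Cycle 4 onward fall under discontinuation, and Section 6.1.1 lists haematology no later than the 30-day visit. Counts alone would in any case give no marrow, subtype or AML status.
- **Importance.** TTP and PFS are absent from the endpoint lists in Section 5.2, and the primary aim is to test the signature. No primary conclusion depends on them. This stands and limits the weight of the point, but it does not make the two objectives estimable.

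**Conclusion.** The concern holds in a limited form. Followed as written, the plan loses progression data after about week 16 in a way that depends on response, and no analysis rule deals with it. If the MDS 002 rates apply, about 32 to 41 of 56 patients (57–74%) would stop at week 12, and roughly 46–69% of all enrolled would have later progression unobserved under assumed median TTP of 12 to 36 months. Whole-cohort TTP and PFS are then likely, not certain, to be too favourable. Deaths are captured, so overall survival is not affected by this gap.

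The count also depends on what counts as stable disease. Section 8.4 places every patient below partial remission without progression there, which, read literally, would include patients with haematologic improvement only. That definition and the statement that responders continue need to be reconciled.

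**What to change.** 1. Add disease status to the 3-monthly contact in Section 6.8 and the Section 2 schedule, for all treated patients: progression by the Section 8 criteria, AML transformation, date, and source of evidence (counts, transfusion record, marrow, clinical report).
2. Define TTP and PFS in Section 11. Analyse all treated patients, with no automatic censoring at the week-12 treatment stop.
3. Add sensitivity analyses that censor at the start of new anti-cancer treatment, and that count it as an event.
4. If disease status is not collected, do not report whole-cohort TTP or PFS. Report overall survival, and limit progression results to time on study in responders.

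The cost is a few CRF fields at contacts that already take place, plus the effort of obtaining local records. No treatment rule changes. The weakness is that, with no protocol marrow after discontinuation, marrow-based progression will be found only where local testing was done. Responders have no scheduled on-treatment marrow either. The report should state this uneven ascertainment as a limitation.

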## **7 Adverse events**

### **7.1 Serious Adverse Event (SAE) Definition**

A serious adverse event is one that at any dose (including overdose):

- Results in death
- Is life-threatening
- Requires inpatient hospitalization or prolongation of existing hospitalization
- Results in persistent or significant disability or incapacity
- Is a congenital anomaly or birth defect
- Is an important medical event
- Suspected positive Pregnancy

“Life-threatening” means that the subject was at immediate risk of death at the time of the serious adverse event; it does not refer to a serious adverse event that hypothetically might have caused death if it were more severe.

“Persistent or significant disability or incapacity” means that there is a substantial disruption of a person’s ability to carry out normal life functions.

Medical and scientific judgment should be exercised in deciding whether expedited reporting is appropriate in situations where none of the outcomes listed above occurred. Important medical events that may not be immediately life-threatening or result in death or hospitalization but may jeopardize the patient or may require intervention to prevent one of the other outcomes listed in the definition above should also usually be considered serious. Examples of such events include allergic bronchospasm requiring intensive treatment in an emergency room or at home, blood dyscrasias or convulsions that do not result in inpatient hospitalization, or the development of drug dependency or drug abuse.

A new diagnosis of cancer during the course of a treatment should be considered as medically important.

## **7.2 Adverse Drug Reaction Reporting**

Toxicity will be scored using CTCAE Version 3.0 for toxicity and adverse event reporting. A copy of the CTCAE Version 3.0 can be downloaded from the CTEP homepage (<HTTP://CTEP.INFO.NIH.GOV>). All appropriate treatment areas should have access to a copy of the CTCAE Version 3.0. All adverse clinical experiences, whether observed by the investigator or reported by the patient, must be recorded, with details about the duration and intensity of each episode, the action taken with respect to the test drug, and the patient's outcome. The investigator must evaluate each adverse experience for its relationship to the test drug and for its seriousness.

The investigator must appraise all abnormal laboratory results for their clinical significance. If any abnormal laboratory result is considered clinically significant, the investigator must provide details about the action taken with respect to the test drug and about the patient's outcome.

### **Severity Ratings:**

The investigator will evaluate the severity of each adverse experience using the following definitions:

- **Mild:** event may be noticeable to the patient, does not influence daily activities, usually does not require intervention.
- **Moderate:** event may be of sufficient severity to make subject uncomfortable; performance of daily activities may be influenced; intervention may be needed.
- **Severe:** event may cause severe discomfort; usually interferes with daily activities; subject may not be able to continue in the study; treatment or other intervention usually needed.

### **Relationship to Study Drug:**

- **Probably Related**  
An adverse event which might be due to the use of the drug. The relationship in time is suggestive. An alternative explanation is less likely, e.g. concomitant drug(s), concurrent disease(s).
- **Possibly Related**  
An adverse event which might be due to the use of the drug. The relationship in time is reasonable; therefore, a causal relationship cannot be excluded. An alternative explanation is inconclusive, e.g. concomitant drug(s), concurrent disease(s).
- **Not Related**

An adverse event which is judged to be clearly due only to extraneous causes (disease, environment, etc.). The cause must be noted on the AE CRF.

### **7.2.1 Pregnancies**

Pregnancies occurring while the subject is on lenalidomide or within 4 weeks after the subject's last dose of lenalidomide are considered expedited reportable events. If the subject is on lenalidomide, it is to be discontinued immediately and the subject is to be instructed to return any unused portion of lenalidomide to the Investigator. The pregnancy must be reported to Celgene Drug Safety within 24 hours of the Investigator's knowledge of the pregnancy by phone and facsimile using the SAE Form.

The Investigator will follow the subject until completion of the pregnancy, and must notify Celgene Drug Safety of the outcome as specified below. The Investigator will provide this information as a follow-up to the initial SAE.

If the outcome of the pregnancy meets the criteria for immediate classification as a SAE (i.e., spontaneous abortion [any congenital anomaly detected in an aborted fetus is to be documented], stillbirth, neonatal death, or congenital anomaly), the Investigator should follow the procedures for Expedited Reporting of SAEs to Celgene (i.e., report the event to Celgene Drug Safety by facsimile within 24 hours of the Investigator's knowledge of the event).

Any suspected fetal exposure to lenalidomide must be reported to Celgene within 24 hours of being made aware of the event. The patient should be referred to an obstetrician/gynecologist experienced in reproductive toxicity for further evaluation and counseling.

All neonatal deaths that occur within 30 days of birth should be reported, without regard to causality, as SAEs. In addition, any infant death after 30 days that the Investigator suspects is related to the *in utero* exposure to lenalidomide should also be reported.

In the case of a live "normal" birth, Celgene Drug Safety should be advised as soon as the information is available.

### **7.3 Investigator Reporting Responsibilities**

The conduct of the study will comply with all FDA safety reporting requirements.

#### IND Annual Reports

If the FDA has granted an IND number, it is a requirement of 21 CFR 312.33, that an annual report is provided to the FDA within 60-days of the IND anniversary date. 21 CFR 312.33 provides the data elements that are to be submitted in the report. The Annual Report should be filed in the study's Regulatory Binder, and a copy provided to Celgene Corporation as a supporter of this study as follows.

Celgene Corporation  
Attn: Medical Development  
[name]  
[name]  
[contact]

All adverse experience reports must include the patient number, age, sex, weight, severity of reaction (mild, moderate, severe), relationship to study drug (probably related, unknown relationship, definitely not related), date and time of administration of test medications and all concomitant medications, and medical treatment provided. The investigator is responsible for evaluating all adverse events to determine whether criteria for "serious" and as defined above are present. The investigator is responsible for reporting adverse events to Celgene as described below.

#### **7.3.1 Expedited reporting by investigator to Celgene**

Serious adverse events (SAE) are defined above. The investigator must inform Celgene in writing with a Celgene SAE form or MEDWATCH 3500A of any SAE within 24 hours of being aware of the event. The date of awareness should be noted on the report. This written report must be completed and supplied to Celgene by facsimile within 24 hours/1 business day at the latest on the following working day. The initial report must be as complete as possible, including details of the current illness and (serious) adverse event, and an assessment of the causal relationship between the event and the investigational product(s). Information not available at the time of the initial report (e.g., an end date for the

adverse event or laboratory values received after the report) must be documented on a follow-up report. A final report to document resolution of the SAE is required. The Celgene tracking number (RV-MDS-PI-388) and the institutional protocol number should be included on SAE reports (or on the fax cover letter) to Celgene. A copy of the fax transmission confirmation of the SAE report to Celgene should be attached to the SAE and retained with the patient records.

### **7.3.2 Report of Adverse Events to the Institutional Review Board**

The principal Investigator is required to notify his/her Institutional Review Board (IRB) of a serious adverse event according to institutional policy.

### **7.3.3 Investigator Reporting to the FDA**

Adverse drug reactions that are **Serious, Unlisted/unexpected, and at least possibly associated to the drug**, and that have not previously been reported in the Investigators brochure, or reference safety information document should be reported promptly to the Food and Drug Administration (FDA) in writing by each investigator/physician engaged in clinical research. A clear description of the suspected reaction should be provided along with an assessment as to whether the event is drug or disease related.

The investigator/physician shall notify the FDA by telephone or by fax of any unexpected fatal or life threatening experience associated with the use of the drug. As soon as possible, but no later than 7 calendar days after the sponsors initial receipt of the information. Each phone call or fax shall be transmitted to the FDA new drug review division in the Center for Drug Evaluation and Research or the product review division in the Center for Biologics Evaluation and Research that has responsibility for review of the IND if applicable.

## **7.4 Adverse event updates/IND safety reports**

Celgene shall notify the Investigator via an IND Safety Report of the following information:

- Any AE associated with the use of study drug in this study or in other studies that is both serious and unexpected.
- Any finding from tests in laboratory animals that suggests a significant risk for human subjects including reports of mutagenicity, teratogenicity, or carcinogenicity.

The Investigator shall notify his/her IRB/EC promptly of these new serious and unexpected AE(s) or significant risks to subjects.

The Investigator must keep copies of all AE information, including correspondence with Celgene and the IRB/EC, on file (see Section 11.4 for records retention information).

